Aim 1. Determine impact of DOMS pain on demand for alcohol and marijuana and examine race and sex as moderators of this relationship.

We predict that those who undergo the DOMS induction paradigm will show greater increases in alcohol and marijuana demand than participants in the sham DOMS control group. We also predict an interactive effect of race and sex on DOMS-related changes in alcohol and marijuana demand, such that increases may be greater in White men than Black women and men, as well as White women.

Aim 2. Identify psychosocial factors associated with change in demand for alcohol and marijuana after DOMS induction.

Consistent with current evidence,^{42, 67} we predict that pain-related negative affect will mediate the association between DOMS-related pain and increased demand for alcohol and marijuana. We also predict that greater expectancy of analgesia from marijuana or alcohol use, higher negative urgency, and history of self-medication behaviors will predict greater change in alcohol and marijuana demand.

6. Research Plan:

Participants

We will recruit participants aged 21 years and older who are regular co-users of alcohol and marijuana (i.e., concurrent or simultaneous use at least 2-3 times per week over the past 6 months). Extent of co-use will be determined using the Alcohol Use Disorders Identification Test (AUDIT) and Cannabis Use Disorder Identification Test, Revised (CUDIT-R). A research team member will inform participants of inclusion and exclusion criteria via email or the phone. If an individual believes they meet all study criteria, they will be scheduled for the first study session (see Phone and Email Scripts for details). We will review all inclusion and exclusion criteria one additional time with participants before initiating the Informed Consent process.

Inclusion/Exclusion Criteria

Detailed inclusion/exclusion criteria are provided in Table 1.

Table 1. Inclusion and exclusion criteria
Inclusion Criteria 
• Aged 21-65 years;• English-speaking• Self-identify as White/Caucasian or Black/African American• Own a smartphone with cellular/data plan• Regularly co-use alcohol and smoked marijuana as indicated by scores of ≥ 3 on item 1 of the CUDIT-R and AUDIT.• Willing and able to give informed consent

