Hypotheses for DOMS-related changes in alcohol and marijuana demand indices (persistence and amplitude) will be assessed using separate 2 (group: DOMS vs. sham DOMS) x 2 (sex: men vs. women) x 2 (race: White vs. Black) x 2 (time: visit 1 vs. visit 2) repeated measures analysis of variance (ANOVA). Identical ANOVAs will examine changes in marijuana demand indices.

Aim 2: Identify psychosocial factors associated with change in demand for alcohol and marijuana after DOMS induction.

To test the hypothesis that negative affect mediates the relationship between DOMS pain and increased alcohol and marijuana demand, Pearson correlations will be conducted to examine continuous relationships between measures of pain, pain-related negative affect (e.g. pain experience VASs), and change in alcohol and marijuana demand. A series of linear regressions will then be conducted to examine 1) the effect of group (DOMS vs. sham DOMS) on change in alcohol and marijuana demand, and 2) the effect of group and pain-related negative affect on change in alcohol and marijuana demand. We will test the significance of indirect effects of pain-related negative affect using PROCESS, a custom macro in SPSS.

To examine the hypothesis that greater expectancy of analgesia from marijuana or alcohol use, higher negative urgency, and history of self-medication behaviors will predict greater change in demand, a simultaneous multiple linear regression analysis will be conducted with these variables as predictors in the model.

Power Analysis

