Effect size estimates for this study were derived from an interim analysis of data from an ongoing pilot project that examined the effect of DOMS on alcohol demand (N=40). In our pilot work, alcohol demand was assessed using the Alcohol Purchase Task (APT) before and after DOMS induction. Amplitude and persistence were derived from APT data using principal components analysis,⁸³⁻⁸⁴ and these factors explained approximately 89% of the variance in alcohol demand metrics. Changes in amplitude and persistence were examined using separate 2 (group: sham vs. DOMS) x 2 (time: time 1 vs. time 2) x 2 (sex: men vs. women) repeated measures ANOVAs. Results indicated sex x group x time interactions for both factors, such that DOMS tended to increase amplitude in men and decrease amplitude in women, $F(1,36)=3.13$, $p=.09$, partial eta squared=.08. A similar pattern of effects was found for persistence where DOMS decreased persistence in women and increased persistence in men, $F(1, 36) = 14.55$, $p=.001$, partial eta squared=.29. With power analyses conducted in G*Power ($\alpha=.05$, power=.80, correlation between repeated measures=0.5), we expect that a proposed sample size of 56 participants will be sufficient to achieve the objectives of the proposed research and have adequate sensitivity to detect medium between-group and interactive effects for which we do not have preliminary data.

7. Possible Discomforts and Risks:

Psychological Discomforts and Risks. Participants may be reminded of unpleasant emotions or experience negative thoughts or bodily sensations while reporting aspects of their current psychosocial functioning or medical history. To mitigate this risk, all participants will be informed they can withdraw from the study at any time or skip individual questions that may be upsetting to them.

Induction of Muscle Pain using Exercise: There is a low risk that exertional rhabdomyolysis (breakdown of muscle tissue due to damage) and myoglobinuria (a large amount of muscle proteins in the urine) may occur following eccentric exercise. However, research suggests that this occurs primarily if a person had not consumed enough fluids before multiple muscle groups are exercised eccentrically.⁸⁷⁻⁸⁸ We will address this risk by instructing participants to remain well-hydrated 24 hours prior to DOMS induction.

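### Aim 1 tests a race-by-sex effect across eight between-subject cells with N = 56, but neither recruitment nor allocation is set up to fill those cells evenly

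*Combined protocol and SAP*

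**What the plan says.** Section 5 (Aim 1) predicts that race and sex interact in the demand response to DOMS, with larger increases in White men than in the other three race-by-sex groups. The Data Analysis Strategy tests this in ANOVAs that cross arm and time with "2 (sex: men vs. women) x 2 (race: White vs. Black"; the same layout is used for alcohol and for marijuana. SPSS 25 is named, but no type of sum of squares.

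On enrolment, the Participants section says "We will recruit participants aged 21 years and older who are regular co-users of alcohol and marijuana". Table 1 limits eligibility to people who identify as White or Black. Neither gives a number, share or cap by race or sex. Arms are assigned under Screening Measures from a spreadsheet list ordered with Excel's random number function. No strata or blocks are mentioned, and the ratio is not stated.

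The Power Analysis says that "a proposed sample size of 56 participants will be sufficient to achieve the objectives of the proposed research" and claims "adequate sensitivity to detect medium between-group and interactive effects" where no pilot data exist. It does not mention cell sizes, expected mix or dropout. Figure 2 (study design) is not available to this review; the text carries no cell numbers.

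**The concern.** Eight cells share 56 people, so an even fill is 7 per cell. Nothing in the plan secures that, and restricting eligibility to two races does not make the two equally common among those who enrol.

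Two things are at stake. First, the predicted contrast of White men with the other three groups needs usable numbers in every cell, and a scarce group could leave a few people per arm to carry it. Second, in a full factorial with Type III tests each effect compares unweighted cell means. A thin cell therefore inflates the variance of every group-by-time term, including the plain group x time term, and not only the race terms.

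**Working it through.** **Inputs from the documents.** N = 56, alpha .05, power .80, "correlation between repeated measures=0.5", and pilot partial eta squared .08 (amplitude) and .29 (persistence), all from the Power Analysis; the 2 x 2 x 2 between-subject layout is from the Data Analysis Strategy.

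**Assumptions.** 1:1 allocation, Type III tests in the full factorial, no dropout, sexes even, and f = .25 for a medium effect. The Black share is varied because no mix is given.

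**1. The plan's 56.** G*Power's within-between convention has noncentrality lambda = f² x N x m/(1 - rho), with m = 2 and rho = .5, so lambda = 4f²N. Partial eta squared .08 gives f² = .08/.92 = .087, so f = .295. With eight groups and 7 numerator df, the smallest N for power .80 is 49. Rounded up to a multiple of eight it is 56, i.e. 7 per cell, with power .87. The plan does not state f, the number of groups or the df, so this route is inferred; at least one other also rounds to 56.

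**2. Variance under imbalance.** For the difference between two averages of four cell means, variance = (sigma²/16) x sum(1/n), where sigma² is the variance of the change score. With 7 per cell, sum(1/n) = 8/7 = 1.143. With Black share p, four cells have 56p/4 people and four have 56(1 - p)/4. The variance factor is then 1/(4p(1 - p)), and effective N = 56 x 4p(1 - p). At p = .25: 4/3.5 + 4/10.5 = 1.524; 1.524/1.143 = 1.33; 56/1.33 = 42.

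Inverting the design matrix for whole-number cells 4, 3, 3, 4, 10, 11, 11, 10 gives a factor of 1.35 for every full-factorial term, group x time included. With sex and race entered additively, the factor for group is 1.00.

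**3. Power for a 1-df group-by-time term, F(1, 48).** Column A starts from a term with exactly .80 power when balanced (lambda = 8.175). Column B uses f = .25 in the G*Power convention (lambda = 4 x .0625 x 56 = 14). Both lambdas are multiplied by 4p(1 - p).

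| Black share | Expected small cell | Variance factor | Effective N | A | B |
|---|---|---|---|---|---|
| 50% | 7.0 | 1.00 | 56 | .80 | .96 |
| 40% | 5.6 | 1.04 | 54 | .78 | .95 |
| 30% | 4.2 | 1.19 | 47 | .73 | .92 |
| 25% | 3.5 | 1.33 | 42 | .68 | .89 |
| 20% | 2.8 | 1.56 | 36 | .61 | .83 |
| 15% | 2.1 | 1.96 | 29 | .52 | .74 |

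Column B crosses .80 at about 18% Black.

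**4. Chance on top of the mix (simulation).** With the simple list, some cell has 3 or fewer people in 47% of draws at 50% Black, 62% at 40%, 89% at 30% and 97% at 25%. At 25% Black, the chance of a cell of 2 or fewer is 80% and of an empty cell 10%. Stratified allocation without enrolment targets lowers these to about 50% and 1%.

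**5. Remedies compared.** Fourteen per race-by-sex group with the simple list gives a median smallest cell of 4 and a cell of 3 or fewer in about 21% of draws. Adding stratified allocation gives 7 in each cell and a factor of 1.00. Restoring balanced precision by size alone would take about 56 x 1.33 = 75 people at 25% Black, or 56 x 1.56 = 87 at 20%.

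**The case against.** Four points against a stronger reading carry weight.

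- **The mix is assumed.** A reader might infer that cells of two or three are the expected outcome. The documents give no mix. Expected cells that small arise only at about 15-25% Black; at 40% the variance loss is about 4%.
- **The .80 starting point is a choice.** A reader might infer that the lead DOMS test fails. With f = .25 in the G*Power convention, it stays above .80 down to about 18% Black. That f is also an assumption. If partial eta squared .08 is read as an observed ANOVA effect (lambda = .087 x 56 = 4.87), power is .58 even when balanced and .47 at 25% Black. Most of that shortfall comes from sample size, not from the mix.
- **Empty cells are largely an allocation matter.** A reader might blame recruitment for the risk that the four-way term cannot be estimated. At 25% Black, stratifying the list alone cuts that risk from 10% to about 1%.
- **The cost to the lead test depends on an unstated analysis choice.** An additive model avoids it. However, that model weights the effect by the enrolled mix. Section 5 predicts moderation, and the pilot showed opposite directions in men and women, so the quantity estimated changes.

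What stands is that no target exists, the layout is fixed in every Aim 1 model, and stratified allocation alone cannot supply people who were not enrolled.

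**Conclusion.** The point holds as a weakness in how the design supports its own Aim 1 hypothesis. The main harm is to the race-by-sex prediction, which may rest on a few people per cell. The plain group x time test mostly loses precision: effective N is about 54 at an assumed 40% Black and 29 at 15%, against 56 if balanced.

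The variance factors are exact given Type III tests in the full factorial, even sexes and arms, and expected cell sizes; random allocation and dropout would make them worse. The documents do not support saying that the lead test is underpowered because of the mix, or that an empty cell is likely because of recruitment. Nor can the review exclude that Figure 2 carries cell numbers. Imbalance cannot be undone once enrolment closes, so this should be changed while recruitment can still be steered.

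**What to change.** Keep N = 56. Enrol to 14 in each of the four race-by-sex groups (White men, White women, Black men, Black women), closing each when full, and stratify the allocation list by race and sex so that each cell has 7. Both parts are needed: a target without strata leaves uneven cells, and strata without a target leave a scarce group scarce.

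Report the eight cell sizes. If a group falls short, give the group x time estimate from a model with sex and race entered additively as a supplementary result, and state that it weights the effect by the enrolled mix.

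The cost is protocol wording, a counter in the screening log and a stratified list. The last group may fill slowly, and some eligible people will be turned away under criteria that are already narrow. The documents give no accrual figures, so how slowly cannot be judged from them.

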Exclusion Criteria 
• Participation in exercises that involve the biceps in the past 6 months*• Self-reported wrist/hand, elbow, or shoulder pain the past 3 months• Chronic medical condition that may affect pain perception (e.g. diabetes, fibromyalgia, headaches)• Self-reported kidney dysfunction, muscle damage, or major psychiatric disorder• Medical marijuana prescription, recommendation, or card• Consumption of marijuana using only non-inhalational methods (e.g. edibles, tinctures, or cannabidiol oil)• Women who are pregnant, trying to become pregnant, or breastfeeding

*Examples include bicep curls, pull-ups, olympic weightlifting, etc.

In addition, participants who indicate they have consumed of any drugs (e.g., alcohol, theophylline, tranquilizers, over-the-counter and prescription pain medications, including NSAIDs and opioids) that may affect pain perception or hydration status 24 hours before participation in a testing session or used caffeine 4 or less hours before testing session will be discontinued or rescheduled at the PI's discretion. Additionally, participants who report that they have used any tobacco products less than 1 hour before participation in a testing session will be discontinued or rescheduled at the PI's discretion.

Screening Procedure

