Screening assessment procedures will take place in a private exam room within the Center for Pain Research and Behavioral Health. Participants will be given a choice of completing the informed consent process with paper documents or electronically via REDCap. The consent process will take place in person, regardless whether it is documented on paper or electronically. After providing informed consent, participants will complete a series of surveys as part of the assessment on a secured laptop computer or tablet, using REDCap. These measures are intended to both address study aims and characterize the sample. All participants will be provided with a pamphlet containing information about local mental health services; if desired, the PI or research assistant will facilitate contact with clinical services. The Patient Health Questionnaire-9 is a well-validated and widely used measure of depressive symptomatology, including suicidal ideation/intent. Responses on the Patient Health Questionnaire-9 regarding suicidal intent will be reviewed by the study team prior to the participant leaving the sight of the study team. Any subjects endorsing suicidal intent during screening will be withdrawn from the study. [name], who is a licensed clinical psychologist, will then provide appropriate referral (e.g. Crisis Hot Line referral, or direct referral to clinical services if deemed appropriate). Women of childbearing potential will also be given a pregnancy test. A positive result will be exclusionary and if desired, the investigative team will facilitate referral for medical care.

Screening Measures

Participants will provide demographics and medical history information, including racial identity and whether they are pregnant, trying to become pregnant, or breastfeeding. They will also complete questionnaires related to mood (Patient Health Questionnaire-9,⁶⁸ Generalized Anxiety Disorder 7-item scale⁶⁹), attitudes about pain (Pain Anxiety Symptoms Scale,⁷⁰ Pain Catastrophizing Scale,⁷¹ Fear of Pain Questionnaire,⁷² Discomfort Intolerance Scale⁷³), somatization (Pennebaker Inventory of Limbic Languidness⁷⁴), and recovery from difficult life events (Brief Resilience Scale⁷⁵).

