Participants who continue to qualify following completion of screening procedures and agree to proceed will be assigned to either the *DOMS* or *Sham DOMS* group. Assignments will be made according to a participant's unique subject identifier using a spreadsheet listing group assignment in pseudo-random order using the Excel random number function.

Participants will then complete the Alcohol Purchase Task (APT), Marijuana Purchase Tasks, (MPT), and DOMS or sham DOMS induction procedures. They will also be will be scheduled for a second lab session 48 hours later so that potential changes in DOMS-associated alcohol and marijuana demand can be investigated. Participants who complete the screening but either do not qualify or decide not to proceed will be paid \$15 via gift card. Those who do qualify and proceed with the study will be paid \$50 at the end of the first lab visit and \$15 at the end of the second lab visit. For the daily surveys, compensation was provided as a function of the number of surveys completed, with a maximum of \$30 for participants who completed 5/7 or more of their assessments (see "Daily Measures" section for additional information). We will also ask whether their DOMS (if any) has resolved with the daily measures. Additionally, participants who refer an individual to the study that attends the screening session will also receive \$20 per person referred. The referee(s) will be responsible for contacting the study team via phone or email in order to schedule the session. The referrer will receive the \$20 bonus once the person they refer attends their screening session, whether or not they eventually decide to participate. All participants who provide informed consent will be eligible to refer participants to the study regardless of whether they qualify to proceed after screening procedures.

Alcohol Purchase Task (APT) and Marijuana Purchase Tasks (MPT)

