Participant Confidentiality Risks. The research team places a high priority on protection of participant confidentiality and will do so using the following procedures. Unique participant identifiers will be generated in order to collect protected health information (i.e., from questionnaires) for research purposes. All data will be stored in encrypted, password-protected files on a secure server, and access to the data will be restricted to research staff. The devices used to collect self-report data will be double-encrypted: the devices and REDCap software used to collect and store the information will be both password-protected and stored in a locked room. Data that links the participant to their unique identifiers will be stored in a separate location. When the study is completed and all data is in an electronic database, participant identifiers will be destroyed. Any

adverse events will be reported to the University of Florida IRB and study sponsors as appropriate. Despite these procedures, it is possible that participant confidentiality may be breached. If a breach occurs, it will be reported to the IRB and appropriate measures will be taken. These measures include but are not limited to informing affected participants of the breach and assisting with protective measures once the breach is detected.

8. **Possible Benefits:** There are no potential benefits to participants in this study.
9. **Conflict of Interest:** There is no conflict of interest involved with this study beyond the professional benefit from academic publication or presentation of the results.
10. **Data Safety Monitoring Plan:** Because the study does not comprise a clinical trial, a formal Data and Safety Monitoring Board has not been planned. The investigative team will meet quarterly to discuss data and safety monitoring issues. Any issues identified during the course of these meetings will be handled in a manner consistent with the University of Florida's policies.

11. References:

1. Institute of Medicine (US) Committee on Advancing Pain Research, Care, and Education. *Relieving Pain in America: A Blueprint for Transforming Prevention, Care, Education, and Research*. Washington (DC): National Academies Press (US); 2011. <http://www.ncbi.nlm.nih.gov/books/NBK91497/>. Accessed November 27, 2019.

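### The arm is looked up by a subject identifier that appears to be in use during screening, and nothing described keeps staff from knowing it before entry is settled

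*Combined protocol and SAP*

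**What the plan says.** All references are to the combined protocol and SAP.

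- **Timing of assignment** (section 6, end of Screening Measures). The sentence beginning "Participants who continue to qualify following completion of screening procedures and agree to proceed will be assigned to either the" goes on to name the DOMS and sham DOMS groups.
- **Method of assignment** (next sentence). "Assignments will be made according to a participant's unique subject identifier using a spreadsheet listing group assignment in pseudo-random order"; the order comes from Excel's random number function.
- **Purpose of the identifier** (section 7, Participant Confidentiality Risks). "Unique participant identifiers will be generated in order to collect protected health information (i.e., from questionnaires) for research purposes". The same paragraph restricts access to study data to research staff, without distinguishing roles.
- **When questionnaires are completed** (section 6, Screening Procedure). "After providing informed consent, participants will complete a series of surveys as part of the assessment on a secured laptop computer or tablet, using REDCap".
- **Discretion** (section 6, text after Table 1). People who report recent use of certain drugs, caffeine or tobacco before a testing session "will be discontinued or rescheduled at the PI's discretion".
- **Checks before consent** (section 6, Participants). All inclusion and exclusion criteria are gone through once more with the person before the consent process begins.

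The text does not say who generates or holds the spreadsheet, whether the screening staff or the PI can open it, or whether arms are released one at a time. It describes no separate randomisation number and no blinding of staff. Figure 2, the design flowchart, is not reproduced in the text available, so it could not be checked.

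**The concern.** Randomisation protects against selection only if nobody who influences entry can know the next assignment. A list filled in beforehand and keyed to a number that the person already carries does not give that protection. Anyone with the list and the number can read the arm.

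The two arms differ openly in burden: three sets of 15 eccentric repetitions against one set of 15 concentric repetitions at 30% of maximum voluntary contraction. Staff could have well-meant reasons to treat a borderline candidate differently according to the arm that is coming.

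Aim 1 makes a causal claim about pain and demand. Aim 2 itself expects analgesia expectancy, negative urgency and a history of self-medication to predict change in demand. If entry differed by arm on traits like these, the group-by-time effect would mix the effect of pain with the effect of selection. The planned ANOVA contains only group, sex, race and time, so it would not adjust for such a difference.

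**Working it through.** No figure in the plan bears on this point, and the sample size of 56 does not enter the argument. The check is a comparison of sections.

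**1. Is the arm fixed before it is applied?** Yes, by the method described. The spreadsheet lists assignments, and the subject identifier selects the entry. Once a person has an identifier, the arm is determined; the later act of assignment only reads it off.

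**2. Does the identifier exist before entry is settled?** This is inferred, not stated.
- Section 7 says that identifiers are generated so that questionnaire information can be collected.
- Screening Procedure has the questionnaires completed in REDCap after consent and before assignment.
- Some of these questionnaires themselves decide eligibility. Table 1 requires a score of at least 3 on item 1 of both the AUDIT and the CUDIT-R, and both instruments are listed under Screening Measures. Suicidal intent reported on the PHQ-9 during screening leads to withdrawal.
- If the questionnaire data carry the identifier, as section 7 implies, the identifier is in use while eligibility is still open.

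**3. Is anything described that keeps the arm hidden in that interval?** No. The only stated limit is that data access is confined to research staff, a group that includes those who screen.

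**4. Where could knowledge of the arm affect who enters?** Taking the steps in order:

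| Step | Room for judgement |
|---|---|
| Criteria review before consent | Some, but it precedes the questionnaires and so, on the same inference, the identifier |
| AUDIT and CUDIT-R item 1, suicidal intent, pregnancy test | Little; rule-bound |
| Medical history: conditions that might alter pain perception, major psychiatric disorder | Some; the terms are open-ended |
| Recent drug, caffeine or tobacco use | The PI chooses between discontinuing and rescheduling |
| Agreement to proceed | Some; it follows contact with staff |

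**5. Can the bias be sized?** No. Bias in demand change would be the difference between arms in some trait produced by selective entry, multiplied by that trait's relation to change. The documents give neither quantity.

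**The case against.** The strongest reply is that the plan places assignment after screening, that criteria are reviewed before consent, and that several later checks are rule-bound. On this view little is left to steer, and the text is merely silent on who holds the list. Much of this stands. The pre-consent review and the fixed checks narrow the opening. Neither the time at which the identifier is issued nor staff access to the list is stated. But the order of steps is not concealment: assigning late does not hide an arm that can be looked up early.

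Four stronger readings are tempting, and the documents do not support them.

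- **That staff do know the arms, or that entry was steered.** The text does not say that anyone who screens opens the list. The finding is a missing safeguard.
- **That the PI could admit a recent user due for sham while deferring one due for DOMS.** The natural reading of the rule offers two outcomes, discontinue or reschedule; testing that day is not among them. A rescheduled person is not excluded and would keep the same identifier, hence the same arm. What remains is arm-dependent discontinuation. The rule also applies at the second visit, where concealing the allocation would not help.
- **That screen failures use up list positions and destroy balance.** No blocking, stratification or forced ratio is described. With simple randomisation, skipping entries independently of arm leaves a valid random sequence.
- **That a serious bias in the outcome can be quantified.** Any figure would need an invented steering rate and trait. The outcome is also within-person change, so stable differences in demand level cancel; only traits related to change would matter.

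**Conclusion.** The point holds as a weakness in the allocation method. As written, the plan lets the arm be known before eligibility and agreement are final, and it describes nothing to prevent this.

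The conclusion rests on two inferences. First, the identifier is issued by the time of the screening questionnaires. Second, with no stated restriction, those who screen or exercise discretion could consult the spreadsheet. Evidence against either, such as a separate randomisation number or an independent list-holder, would remove the concern.

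The opening for selective entry is real but limited, and the size of any bias cannot be calculated from the documents. The change is worth making because it costs little and protects the randomised comparison on which Aim 1 depends.

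**What to change.** Number the allocation list by order of assignment instead of by subject identifier. Load it into the randomisation function of REDCap, which the study already uses, with the list hidden from those who screen and from the PI; or use sequentially numbered sealed envelopes prepared by someone who does not screen. Release one assignment at a time, and only after three items have been recorded: the eligibility decision, the result of the recent-substance check together with any decision to discontinue or reschedule, and the participant's agreement to proceed. State in Screening Measures who generates and who holds the list.

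The cost is a short set-up and one paragraph of protocol text. It adds no visits or procedures and does not change the sample size. If the team already works this way, saying so settles the point.
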